5.4.4.2. Vital Signs and Physical Examination Findings

Continuous vital sign parameters including pulse, blood pressure (systolic and diastolic), and weight will be summarized at each assessment time point. The observed value and change from baseline will be summarized by intervention group. Descriptive statistics (mean, SD, median, minimum, and maximum) will be presented.

Incidence of markedly abnormal vital signs during intervention, as defined in Table 11, will be summarized for participants who had a baseline assessment and at least 1 post-baseline assessment for that vital sign. A listing of participants with markedly abnormal vital signs will be presented.

Table 11: Markedly Abnormal Vital Signs

Vital Sign	Criteria	
Pulse	>120 bpm and with >30 bpm increase from baseline	
	<50 bpm and with >20 bpm decrease from baseline	
Systolic blood pressure	>180 mm Hg and with >40 mm Hg increase from baseline	
	<90 mm Hg and with >30 mm Hg decrease from baseline	
Diastolic blood pressure	>105 mm Hg and with >30 mm Hg increase from baseline	
	<50 mm Hg and with >20 mm Hg decrease from baseline	

5.4.4.3. Electrocardiogram

No analysis is planned.

5.4.4.4. Other Safety Parameters

5.4.4.4.1. Suicidal Ideation and Behavior

The electronic Columbia-Suicide Severity Rating Scale (eC-SSRS) will be used as a screening tool to prospectively evaluate the potential of guselkumab to induce suicidal ideation and behavior. The eC-SSRS defines 5 subtypes of suicidal ideation and behavior in addition to self-injurious behavior with no suicidal intent, and is a fully-structured participant self-report questionnaire, including standardized questions, follow-up prompts, error handling routines, and scoring conventions (Mundt 2013; Posner 2011). Two versions of the eC-SSRS will be used in this study, the Lifetime version and the Since Last Contact version. The Lifetime version will be conducted during the screening visit and the Since Last Contact version will be conducted at all other visits through Week 112.

Participants will complete the eC-SSRS questionnaire using the Sponsor-provided electronic tablets (or through an Interactive Voice Response System, if available). Study site personnel will train the participants on how to use the electronic device and/or a telephone system. The eC-SSRS will be provided in the local languages in accordance with local guidelines.

The eC-SSRS will be performed during each evaluation visit according to the Time and Events schedule. The eC-SSRS should be performed after the joint assessment at the screening visit (after signing informed consent). At Week 0/baseline and at all post-baseline visits, the eC-SSRS will be the first assessment/questionnaire that the participant completes prior to study intervention administration.

At the conclusion of each assessment, the site will receive an eC-SSRS Findings Report from the eC-SSRS vendor. Positive reports are generated from the eC-SSRS vendor for ANY of the following findings:

- Ideation Level 4: Some intent to act, no plan
- Ideation Level 5: Specific plan and intent
- Behaviors: Actual Suicide Attempts
- Behaviors: Interrupted Attempts
- Behaviors: Aborted Attempts
- Behaviors: Preparatory actions

Negative suicidality indication reports are generated from the eC-SSRS vendor when there are NO indications of the above.

Any eC-SSRS findings, which in the opinion of the investigator are new or considered to be worsening and clinically significant, should be reported on the AE eCRF.

Suicidal ideation and behavior will be categorized as follows, with higher scores indicating greater severity:

Suicidal Ideation (1-5)

- 1 =Wish to be Dead
- 2 = Non-specific Active Suicidal Thoughts
- 3 = Active Suicidal Ideation with Any Methods (Not Plan) without Intent to Act
- 4 = Active Suicidal Ideation with Some Intent to Act, without Specific Plan
- 5 = Active Suicidal Ideation with Specific Plan and Intent

Suicidal Behavior (6-10)

- 6 = Preparatory Acts or Behavior
- 7 = Aborted Attempt
- 8 = Interrupted Attempt
- 9 = Actual Attempt (non-fatal)
- 10 = Completed Suicide

The baseline is defined as the most severe/maximum score at screening and Week 0. Suicidal ideation and behavior will be analyzed by the most severe/maximum post-baseline outcome. In addition, a shift table from baseline to post-baseline will also be provided. Participants with positive (ie, score >0) ideation and behavior will be presented in a data listing.

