- 19. Currently has a malignancy or has a history of malignancy within 5 years prior to screening (with the exception of a nonmelanoma skin cancer that has been adequately treated with no evidence of recurrence for at least 3 months prior to the first study intervention administration or cervical carcinoma in situ that has been adequately treated with no evidence of recurrence for at least 3 months prior to the first study intervention administration).
- 20. Has a history of lymphoproliferative disease, including lymphoma; a history of monoclonal gammopathy of undetermined significance; or signs and symptoms suggestive of possible lymphoproliferative disease, such as lymphadenopathy or splenomegaly.
- 21. Is currently undergoing or has previously undergone allergy immunotherapy for a history of anaphylactic reactions.
- 22. Has a transplanted organ (with exception of a corneal transplant >3 months prior to the first administration of study intervention).
- 23. Has known hypersensitivity to any biologic medication, or known allergies or clinically significant reactions to murine, chimeric, or human proteins, mAbs, or antibody fragments.
- 24. Has unstable suicidal ideation or suicidal behavior in the last 6 months, that may be defined as an electronic Columbia-Suicide Severity Rating Scale (eC-SSRS) rating at screening of:
 - Ideation level 4: Some intent to act, no plan; OR
 - Ideation level 5: Specific plan and intent; OR
 - Any of the following suicidal behaviors:
 - Actual suicide attempts
 - Interrupted attempts
 - Aborted attempts
 - Preparatory actions

AND

is confirmed to be at risk by the investigator based on an evaluation by a mental health professional. The final decision on excluding a participant will be made at the judgment of the investigator.

- 25. Has known allergies, hypersensitivity, or intolerance to guselkumab or its excipients (refer to the IB).
- 26. Is pregnant, nursing, or planning a pregnancy (both men and women) within 12 weeks after receiving the last administration of study intervention.
- 27. Has had major surgery (eg, requiring general anesthesia and hospitalization) within 8 weeks prior to screening, or will not have fully recovered from such surgery, or has such surgery planned during the time the participant is expected to participate in the study (52 weeks). Note: Participants with planned surgical procedures to be conducted under local anesthesia may participate.

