At the screening visit, the eC-SSRS should be completed as the first assessment after signing informed consent and joint assessment, but before any other tests, procedures, or other consultations. For subsequent visits, the eC-SSRS should be completed after all PROs and before any other tests, procedures, or other consultations. At the conclusion of each assessment, the eC-SSRS Findings Report can be viewed electronically. At screening ("In the last 6 months") and Week 0, participants with an Ideation level (1-5) or any suicidal behaviors or with a response of "YES" for non-suicidal, self-injurious behavior must be determined to be not at risk by the investigator based on an evaluation by a mental health professional in order to be randomized. Participants with an Ideation level (1-5) on the eC-SSRS or any suicidal behaviors or with a response of "YES" for non-suicidal, self-injurious behavior at any postbaseline visit will also be referred to an appropriate mental health professional for evaluation. If a participant's psychiatric disorder can be adequately treated with psychotherapy and/or pharmacotherapy then the participant, at the discretion of the investigator, should be continued with treatment. Ultimately, the determination of suicidality and risk is up to the investigator's clinical judgment following evaluation by a mental health professional (eg, psychiatrist, psychologist, or appropriately trained social worker or nurse).

Positive reports are generated from the eC-SSRS vendor for ANY of the following findings:

- Ideation level 4: Some intent to act, no plan
- Ideation level 5: Specific plan and intent
- Behaviors: Actual suicide attempts
- Behaviors: Interrupted attempts
- Behaviors: Aborted attempts
- Behaviors: Preparatory actions.

Negative suicidality indication reports are generated from the eC-SSRS vendor when there are NO indications of the above.

The participant should not leave the site at screening or be dosed at dosing visits before the eC-SSRS Findings Report (both for negative and positive reports) is reviewed by the investigator and the participant's risk has been assessed and follow-up determined, as appropriate. For each Ideation level and Behavior, the following actions and associated alerts will be generated, if applicable:

- No ideation with No Behaviors: No further action is needed.
- Ideation Levels (1-5) or suicidal behavior: Participant risk assessed and referral to a mental health professional.

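### The eC-SSRS baseline has no recall limit, so the shift table sets a lifetime worst score against an on-study worst score and cannot reliably show newly emerging ideation or behavior

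*SAP*

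**What the plan says.** SAP Section 5.4.4.4.1 fixes the instrument by visit: "The Lifetime version will be conducted during the screening visit and the Since Last Contact version will be conducted at all other visits". Protocol Section 8.2.7 says the same. Scores run from 1 to 5 for ideation and from 6 to 10 for behavior, with higher scores more severe. The listing rule (score above 0) implies that 0 means no finding.

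The analysis then has three parts:

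- Baseline: "The baseline is defined as the most severe/maximum score at screening and Week 0".
- Main summary: "Suicidal ideation and behavior will be analyzed by the most severe/maximum post-baseline outcome".
- Shift table: "In addition, a shift table from baseline to post-baseline will also be provided".

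Participants with a score above 0 are also listed.

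A shorter recall window appears only in the protocol's eligibility rules. Section 8.2.7 qualifies the screening result with "In the last 6 months" when deciding who needs a mental health evaluation before randomization. Exclusion criterion 24 in Section 5.2 begins "Has unstable suicidal ideation or suicidal behavior in the last 6 months". The SAP does not carry this window into its baseline definition.

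**The concern.** The SAP gives the purpose of the eC-SSRS as judging prospectively whether guselkumab induces suicidal ideation or behavior. Induction is a change from the participant's state shortly before treatment. A lifetime maximum does not measure that state, because it can be set by an event many years old.

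The shift table is the only planned eC-SSRS output that refers to baseline. If its baseline is a lifetime worst score, participants with a remote history enter in a high row. A new on-treatment finding of equal or lesser severity then falls on or below the diagonal. These are participants in whom a new finding would be of particular interest.

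**Working it through.** The SAP gives no figure to reproduce. The check applies its derivation rule to the recall window of each form.

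**Recall windows**

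| Score | Form | Period covered |
|---|---|---|
| Screening, as the SAP uses it | Lifetime | Whole life, no limit stated |
| Screening, as the protocol uses it for eligibility | Lifetime, last-6-months result | 6 months before screening |
| Week 0 | Since Last Contact | Screening to Week 0 |
| Post-baseline maximum | Since Last Contact, worst over visits | Whole on-study period, to Week 112 |

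**Who can enter with an older history.** Exclusion criterion 24 looks back 6 months and also requires that the participant be confirmed at risk. Older ideation or behavior does not exclude under it. Exclusion criterion 17, on severe or uncontrolled psychiatric disturbance, may remove some of these participants, but it does not name past ideation or behavior.

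**Rule.** Let L be the worst lifetime score at screening, R the worst score in the last 6 months at screening, W the Week 0 score and P the post-baseline maximum. L includes the last 6 months, so L ≥ R.

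- SAP baseline as written: max(L, W).
- Recent-window baseline: max(R, W).
- The two differ only when L > max(R, W).

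**Illustration.** All scores are assumed. W = 0 and P = 4 in every row.

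| L | R | SAP rule | Recent window | What the SAP table shows |
|---|---|---|---|---|
| 9 | 0 | max(9, 0) = 9; 9 to 4 | max(0, 0) = 0; 0 to 4 | Lower category |
| 4 | 0 | max(4, 0) = 4; 4 to 4 | 0 to 4 | Unchanged |
| 2 | 0 | max(2, 0) = 2; 2 to 4 | 0 to 4 | Rise, but understated |
| 4 | 4 | 4 to 4 | max(4, 0) = 4; 4 to 4 | Same under both rules |
| 0 | 0 | 0 to 4 | 0 to 4 | Same under both rules |

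Emergence relative to the recent state is therefore:

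- fully masked when max(R, W) < P ≤ L;
- understated when max(R, W) < L < P;
- shown correctly when the lifetime worst score is no higher than the recent one.

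**The case against.** **The window may be an omission and not a choice.** Where the protocol acts on the screening result it uses 6 months, and Section 8.2.7 pairs that result with Week 0, the same two visits as the SAP baseline. The sponsor may intend exactly the baseline proposed here. That is possible, but the SAP does not say so. It names the Lifetime form for screening and then takes the maximum, so a programmer following the text would use the lifetime score.

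**A reader might infer that on-treatment events are hidden.** The documents do not support that. The main summary is the post-baseline maximum, which does not depend on baseline and would count the level 4 participant at level 4. Scores above 0 are listed. Findings that the investigator considers new or worsening and clinically significant go on the adverse event form, and any post-baseline ideation or behavior leads to referral under Protocol Section 8.2.7. What remains is that the summary does not separate new from pre-existing findings, the listing is not aggregated by arm, and the adverse event route rests on judgment.

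**A reader might infer bias between arms.** None is shown. The rule is identical in three randomized, blinded groups, and SAP Section 5.4 plans no formal safety comparison.

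**The SAP labels no cell as improved or worsened.** This is correct. The point concerns where a participant falls in the table. Even on the lifetime reading, a move from 0 usefully identifies first-ever ideation.

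**Conclusion.** The point holds as a limited defect in one descriptive table. As written, the rule sets a lifetime worst score against an on-study worst score, and the only eC-SSRS output referred to baseline cannot reliably show emergence.

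Its reach is narrow. It affects participants whose lifetime worst score exceeds both their last-6-months and Week 0 scores and who then have a post-baseline score above that recent level. It would be wrong to infer that everyone with a lifetime history is affected: those whose worst score is recent are tabulated the same way under either rule. It would also be wrong to describe the mismatch as lifetime against a few weeks, because the post-baseline maximum spans all visits on study. The documents give no frequency, so the number of affected participants cannot be estimated.

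The conclusion assumes that the screening score in the SAP baseline is the Lifetime score, as the text states. If the 6-month result was meant, one clause settles the matter. No endpoint, test or efficacy conclusion depends on it.

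**What to change.** In SAP Section 5.4.4.4.1, define the eC-SSRS baseline for the shift table as the maximum of the last-6-months responses at screening and the Week 0 score. Report lifetime history separately as a baseline characteristic.

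Protocol Section 8.2.7 already relies on the last-6-months result, so no new visit or assessment is needed; the analysis data should be checked to confirm that this result is held as its own field. The cost is a short text edit and one extra baseline summary. The small downside is that the shift table will no longer separate first-ever from recurrent ideation unless it is read alongside lifetime history.

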5.5. Other Analyses

5.5.1. Pharmacokinetics

PK analyses will be performed on the PK analysis set, defined as participants who have received at least 1 complete dose of guselkumab and have at least 1 valid blood sample drawn for PK analysis (Section 4.6). Subjects will be analyzed according to the treatment groups that they actually receive. No imputation for missing concentration data will be performed.

Descriptive statistics (N, mean, SD, median, range, CV (%) and IQ range) will be used to summarize serum guselkumab concentrations at each sampling time point by treatment group. PK data may be displayed graphically. The following analyses will be performed by treatment group as appropriate:

- Summary of serum guselkumab concentrations at each visit by treatment group
- Proportion of subjects without detectable serum guselkumab concentration at each visit by treatment group
- Summary of serum guselkumab concentrations at each visit by treatment group and body weight
- Summary of serum guselkumab concentrations at each visit by treatment group and baseline MTX use (Yes, No)
- Summary of serum guselkumab concentrations by baseline CRP levels
- Plot of median (IQ) serum guselkumab concentrations over time by treatment group

In addition, the relationship between serum guselkumab concentrations and safety or efficacy may be explored.

For summary statistics of serum guselkumab concentrations, concentration values below the LLOQ will be treated as zero. Once a subject meets one of the following dosing deviation criteria, the subject's data will be excluded from the by-visit data analyses from that point onwards.

Dosing deviation criteria:

- Discontinue SC guselkumab administrations.
- Skipped an SC guselkumab administration.
- Received an incomplete/ incorrect SC dose.
- Received an incorrect SC study agent.
- Received an additional SC guselkumab dose.

In addition, if a subject has an administration outside of visit windows (Section 5.1.1), the concentration data collected at and after that visit will be excluded from the by-visit data analyses. Additional exclusions for incongruous PK data to be implemented based on Janssen SOP-07952.

5.5.2. Immunogenicity

The antibodies to guselkumab will be summarized based on all participants who received at least one (complete or partial) administration of guselkumab and who had at least 1 sample obtained after their first administration of guselkumab (Section 4.7). Subjects will be analyzed according to the treatment groups that they actually receive. No imputation for missing concentration data will be performed.

The following analysis of antibodies to guselkumab will be performed by treatment group:

- Summary of antibodies to guselkumab status
- Summary of neutralizing antibodies to guselkumab status
- List of subjects positive for antibodies to guselkumab

In addition, to explore the relationship between antibodies to guselkumab status and serum guselkumab concentrations, efficacy and safety, the following analysis may be performed as appropriate:

- Summary of clinical response (eg, ACR 20 and ACR50, IGA) by antibody to guselkumab Status
- Summary of injection-site reactions by antibody to guselkumab status
- Summary of serum guselkumab concentrations by antibody to guselkumab status
- Plots of median (IQ) trough serum guselkumab concentrations over time by antibody to guselkumab status.

5.5.3. Biomarker/Pharmacodynamic Analysis

Methods and results for biomarker/PD analyses will be presented in a separate technical report.

5.5.4. Pharmacokinetic/Pharmacodynamic Relationships

If data permit, the relationships between serum guselkumab concentration and efficacy may be analyzed graphically. If any visual trend is observed, a suitable population PK/PD model may be developed to describe the exposure-response relationship. Details will be given in a population PK/PD analysis plan and results of the population PK/PD analysis will be presented in a separate technical report.

5.5.5. Definition of Subgroups

To evaluate the consistency in the primary efficacy endpoint (proportion of participants who achieve ACR 20 at Week 24) and the major secondary endpoint over demographics, baseline characteristics, prior and baseline medication use, subgroup analyses will be performed. The subgroups include, but are not limited to, the following:

Subgroup	Variant	Definition
Demographics		
Gender		• Male
		Female
Race		• White
A 1 1' ()		• Other • <45
Age at baseline (year)		• <45 • ≥45 and <65
		• ≥65
Body weight at baseline (kg)	1 (Categories)	• ≤90
, ,		• >90
Body weight at baseline (kg)	2 (Quartiles)	• 1st Quartile: ([##] to [##])
		• 2nd Quartile: ([##] to [##])
		• 3rd Quartile: ([##] to [##])
Body mass index at baseline		4th Quartile: ([##] to [##])Normal [<25]
(kg/m ²)		• Overweight [≥25 to <30]
(kg/m ⁻)		• Obese [≥30]
Participating regions		Eastern Europe (except Russia, Ukraine, Poland)
		North America
		• Poland
		• Russia
		 Ukraine Other countries
		• Other countries
Baseline disease characteristics	5	
PsA duration at baseline (year)		• <1
		• ≥1 to <3
PsA subtype		• ≥3 • distal interphalangeal joint involvement
1 sA subtype		polyarticular arthritis with absence of rheumatoid
		nodules
		asymmetric peripheral arthritis
		spondylitis with peripheral arthritis
Number of swollen joints at		• <10
baseline		• 10 to 15 • >15
Number of tender joints at		• <10
baseline		• 10 to 15
		• >15
HAQ-DI score at baseline		• <1
		• 1 to 2
CDD (1 1' (/IT)	1.(0.4	• >2
CRP at baseline (mg/dL)	1 (Categories)	• <1 • 1-2
		• 1-2 • ≥2
CRP at baseline (mg/dL)	2 (Quartiles)	• 1st Quartile: ([##] to [##])
··· - ··· · · · · · · · · · · · · · · ·	(((• 2nd Quartile: ([##] to [##])
		• 3rd Quartile: ([##] to [##])
		• 4th Quartile: ([##] to [##])
Dactylitis at baseline		• Yes
Enthesitis at baseline		• No
Enthesitis at baseline		YesNo
	1	- 140

Subgroup	Variant	Definition
7.07		
PASI score at baseline		• <12
		• ≥ 12 to ≤ 20
		• ≥20
BSA of psoriasis at baseline		• <3%
		• $\geq 3\%$ to $< 10\%$
		• $\geq 10\%$ to $< 20\%$
		• ≥20%
IGA score at baseline		• <2
		• ≥2
Prior and baseline medication	use	
Reason for discontinuation for		 Efficacy - inadequate response (IR)
prior anti-TNF		Safety - contraindication or intolerance (but not IR)
		• Other
Use of non-biologic DMARDs		• Yes
(MTX, SSZ, HCQ, LEF) at		• No
baseline (based on eCRF)		
Oral corticosteroids at baseline		• Yes
(based on eCRF)		• No
NSAIDs at baseline		• Yes
		• No
Number of prior non-biologic		• 0
treatments including DMARDs,		• 1
systemic immunosuppressive		• 2
drugs, and apremilast		• ≥3
Reason for discontinuation of		Efficacy - inadequate response (IR)
prior DMARDs		 Safety - contraindication or intolerance (but not IR)
		• Other
Note that some of the above su	bgroup cut-off	points may be changed if there are no or few participants within a
subgroup category		

5.6. Interim Analyses

No interim analysis is planned for this study.

5.6.1. Data Monitoring Committee (DMC)

No DMC is planned for this study.

6. SUPPORTING DOCUMENTATION

6.1. Appendix 1: List of Abbreviations

ACR American College of Rheumatology

AE adverse event
ALP alkaline phosphatase
ALT alanine aminotransferase
ANCOVA Analysis of Covariance
AST aspartate aminotransferase

BASDAI Bath Ankylosing Spondylitis Disease Activity Index

BMI body mass index
BSA body surface area
BUN blood urea nitrogen
CI confidence interval
CMH Cochran-Mantel-Haenszel
CRP C-reactive protein

CTCAE Common Terminology Criteria for Adverse Events
DAPSA Disease Activity index for PSoriatic Arthritis

DBL database lock

DMARD Disease-Modifying Antirheumatic Drugs

eCRF electronic case report form

eC-SSRS electronic Columbia-Suicide Severity Rating Scale

EE early escape

FACIT-F Functional Assessment of Chronic Illness Therapy - fatigue

FAS Full Analysis Set

FAS-UKR Full Analysis Set Excluding Ukraine FCS Full Conditional Specifications

GDEV Physician's Global Assessment of Disease Activity
GDPT Patient's Global Assessment of Disease Activity

GGT gamma-glutamyltransferase GLMM Generalized Linear Mixed Model

HAQ-DI HAQ disability index HCQ hydroxychloroquine HRQOL health related quality of life

ICE intercurrent event

IGA Investigator's Global Assessment INR International normalized ratio

IQ interquartile

IR inadequate response

IWRS interactive web response system

LEF leflunomide

LEI Leeds Enthesitis Index LLN lower limit of normal LLOQ lower limit of quantification

LSmeans least squares means

MACE Major adverse cardiovascular events

MAR missing at random
MCS Mental Component Score
MDA Minimal Disease Activity
MI multiple imputation

MMRM Mixed-Effect Model Repeated Measures

MNAR Missing not at random

MTX methotrexate

NCI-CTCAE National Cancer Institute - Common Terminology Criteria for Adverse Events

NR non-responder NRS numeric rating scale

NSAID non-steroidal anti-inflammatory drug

PAIN Patient's assessment of pain

PASDAS Psoriatic ArthritiS Disease Activity Score

PASI Psoriasis Area and Severity Index PCS Physical Component Summary

PD pharmacodynamic(s)
PK pharmacokinetic(s)
PPAS Per-Protocol Analysis Set

PROMIS-29 Patient-Reported Outcomes Measurement Information System-29

PsA psoriatic arthritis

PsAID-12 PsA Impact of Disease-12

q4w every 4 weeks q8w every 8 weeks RA rheumatoid arthritis SAE serious adverse event SAP Statistical Analysis Plan

SC subcutaneous
SD standard deviation
SDV source data verification

SF-36 36-Item Short Form Survey Instrument

SJC Swollen Joint Count

SPARCC Spondyloarthritis Research Consortium of Canada

SSZ sulfasalazine

TEAE treatment emergent adverse event

TF treatment failure(s)
TJC Tender Joint Count
TNF tumor necrosis factor
ULN upper limit of normal
VAS visual analog scale

VLDA Very Low Disease Activity VTE Venous thromboembolism

